5.1.5 Permanent Discontinuation of Ipilimumab

5.1.5.1 Permanent Discontinuation for Related Adverse Events

- Any ≥ Grade 2 eye pain or reduction of visual acuity that does not respond to topical therapy and does not improve to ≤ Grade 1 severity within 2 weeks of starting therapy, OR, requires systemic treatment.
- Any \geq Grade 3 bronchospasm or other hypersensitivity reaction.
- Any other \geq Grade 3 non-skin related adverse event with the exception of events listed under "No Discontinuation" (below).
- Any adverse event, laboratory abnormality or intercurrent illness which, in the judgment of the investigator, presents a substantial clinical risk to the patient with continued dosing.

5.1.5.2 Exceptions to Permanent Discontinuation

- Potentially reversible inflammation (< Grade 4), attributable to a local anti-tumor reaction and a potential therapeutic response. This includes inflammatory reactions at sites of tumor resections or in draining lymph nodes, or at sites suspicious for, but not diagnostic of metastasis.
- Hospitalization for ≤ Grade 2 adverse events where the primary reason for hospitalization is to expedite the clinical work-up.
- Patients with the following conditions where in the investigator's opinion continuing study drug administration is justified:
 - Ocular toxicity that has responded to topical therapy.
 - Endocrinopathies where clinical symptoms are controlled with appropriate hormone replacement therapy. Note: Ipilimumab may not be restarted while the patient is being treated with systemic corticosteroids except for patients on stable doses of hormone replacement therapy such as hydrocortisone.

5.1.6 Immune-Related Adverse Events (IRAEs): Definition, Monitoring, and Treatment

Blocking CTLA-4 function may permit the emergence of auto-reactive T cells and resultant clinical autoimmunity. Rash/vitiligo, diarrhea/colitis, uveitis/episcleritis, hepatitis, and hypopituitarism were drug-related, presumptive autoimmune events, now termed IRAEs, noted in previous ipilimumab studies.

For the purposes of this study, an IRAE is defined as an AE of unknown etiology associated with drug exposure and consistent with an immune phenomenon. Efforts should be made to rule out neoplastic, infectious, metabolic, toxin or other etiologic

causes prior to labeling an AE an IRAE. Serological, immunological, and histological (biopsy) data should be used to support the diagnosis of an immune-mediated toxicity. Suspected IRAEs must be documented on an AE or SAE form.

Patients should be informed of and carefully monitored for evidence of clinically significant systemic IRAE (e.g., systemic lupus erythematosus-like diseases) or organ-specific IRAE (e.g., rash, colitis, uveitis, hepatitis or thyroid disease). If an IRAE is noted, appropriate work-up (including biopsy if possible) should be performed, and steroid therapy may be considered if clinically necessary. See Appendix 3 for suggested work-up and treatment of IRAEs.

It is unknown if systemic corticosteroid therapy has an attenuating effect on ipilimumab activity. However, clinical anti-tumor responses have been maintained in patients treated with corticosteroids and discontinued from ipilimumab. If utilized, corticosteroid therapy should be individualized for each patient. Prior experience suggests that colitis manifested as \geq Grade 3 diarrhea requires corticosteroid treatment. See Appendix 4 for additional details.

5.1.7 Other Guidance

5.1.7.1 Immune-Related Adverse Events Considered to be Related to the ipilimumab

Previous studies have shown that 74% (about 3 in 4) of treated patients develop a side effect of any grade of severity due to the immune system attacking normal cells. About 22% (about 1 in 4) of patients have a serious immune-related adverse event. Serious side effects may be fatal or life-threatening, require you to be hospitalized, may permanently disable you, make you weak and unable to function at your current level, or may put your health at risk or require surgery or intervention by your study doctor.

These immune-related side effects have usually been controlled by stopping the ipilimumab treatment and if needed, with medications, including steroids (medications that are used to decrease inflammation). If you develop an immune-related event, the symptoms may take several months to improve. These immune-related adverse events can relate to: Stomach/Intestine, Rash, Eye, Endocrine Glands, Liver, Other Organs, Meningitis, immune-related motor neuropathy, nephritis, skin disorders and joint pain.

Patients receiving the Ipilimumab sometimes experience a serious skin toxicity, though this is very rare. If a patient develops a skin toxicity, a biopsy is recommended. If a biopsy is done, a portion of it may be sent to an independent doctor for review.

While receiving treatment with the ipilimumab, patients may be at risk of side effects (such as fever, low blood pressure, chills, flushing, nausea and/or vomiting) that occur during or shortly after the infusion (within 24 hours). If these events occur during the infusion, they may be treated by slowing or stopping the infusion, or with treatment such as fluids given into your vein or other common medications. These events can also occur hours after the completion of the infusion.

5.1.7.2 Treatment of Infusion Reactions Associated with Ipilimumab

Since ipilimumab contains only human protein sequences, it is less likely that any allergic reaction will be seen in patients. However, it is possible that infusion of ipilimumab will induce a cytokine release syndrome that could be evidenced by fever, chills, rigors, rash, pruritus, hypotension, hypertension, bronchospasm, or other symptoms. No prophylactic pre-medication will be given unless indicated by previous experience in an individual patient. Reactions should be treated based upon the following recommendations.

- For mild symptoms (e.g., localized cutaneous reactions such as mild pruritus, flushing, rash):
 - Decrease the rate of infusion until recovery from symptoms, remain at bedside and monitor patient.

- Complete the ipilimumab infusion at the initial planned rate.
- Diphenhydramine 50 mg IV may be administered at the discretion of the treating physician and patients may receive additional doses with close monitoring.
- Premedication with diphenhydramine may be given at the discretion of the investigator for subsequent doses of ipilimumab.
- For moderate symptoms (any symptom not listed above [mild symptoms] or below [severe symptoms] such as generalized pruritus, flushing, rash, dyspnea, hypotension with systolic BP >80 mmHg):
 - Interrupt ipilimumab.
 - Administer diphenhydramine 50 mg IV.
 - Monitor patient closely until resolution of symptoms.
 - Corticosteroids may abrogate any beneficial immunologic effect, but may be administered at the discretion of the treating physician.
 - Resume ipilimumab infusion after recovery of symptoms.
 - At the discretion of the treating physician, ipilimumab infusion may_be resumed at one half the initial infusion rate, then increased incrementally to the initial infusion rate.
 - If symptoms develop after resumption of the infusion, the infusion should be discontinued and no additional ipilimumab should be administered that day.
 - The next dose of ipilimumab will be administered at its next scheduled time and may be given with pre-medication (diphenhydramine and acetaminophen) and careful monitoring, following the same treatment guidelines outlined above.
 - At the discretion of the treating physician additional oral or IV antihistamine may be administered prior to dosing with ipilimumab.
- For severe symptoms (e.g., any reaction such as bronchospasm, generalized urticaria, systolic blood pressure <80 mm Hg, or angioedema):
 - Immediately discontinue infusion of ipilimumab, and disconnect infusion tubing from the subject.
 - Consider bronchodilators, epinephrine 1 mg IV or subcutaneously, and/or diphenhydramine 50 mg IV, with solumedrol 100 mg IV, as needed.
 - Patients should be monitored until the investigator is comfortable that the symptoms will not recur.
 - No further ipilimumab will be administered.
- In case of late-occurring hypersensitivity symptoms (e.g., appearance within one week after treatment of a localized or generalized pruritus), symptomatic treatment may be given (e.g., oral antihistamine, or corticosteroids).

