5.1.3 Dose Modifications

Patients may develop study drug-related toxicities that may require skipping doses or dose discontinuation. Some of these adverse events may be consistent with potentially drug-related immune-mediated phenomena; termed IRAEs (Appendix 3). Details of how to dose study medication in the present of adverse drug reactions that may or may not be IRAEs are addressed below.

Treatment modifications will be made based on specified safety criteria. Patients will delay or discontinue treatment with ipilimumab if they experience at least one adverse event, specified below, considered by the investigator to be certainly, probably, or possibly related to ipilimumab treatment. The following criteria will be used to determine dosing delay, restarting doses, or discontinuing ipilimumab.

There are no dose modifications because Ipilimumab is much less effective at lower doses.

Delay ipilimumab dosing for the following related adverse events:

It may be necessary to skip study drug dosing for the following related adverse event(s):

- Any ≥ Grade 2 non-skin related adverse event (including IBEs), except for laboratory abnormalities
- Any ≥ Grade 3 laboratory abnormality.

It is necessary to skip study drug dosing for the following adverse events:

• Any \geq Grade 3 skin-related adverse event regardless of causality.

Restart ipilimumab dosing if/when the adverse event(s) resolve(s) to \leq Grade 1 severity or returns to baseline within 3 weeks of initial dose administration:

- If the *adverse event has resolved*, restart ipilimumab dosing at the next scheduled time point per protocol.
- If the *adverse event has not resolved* in the protocol-specified dosing window (3 weeks [+/- 3 days], the next scheduled dose will be *omitted*.

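### After a resolved infusion-related bronchospasm below Grade 3, Section 5.1.7.2 ends ipilimumab while Section 5.1.3 resumes it on schedule, and neither is said to take precedence

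*Combined protocol and SAP*

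**What the plan says.** Three sections of the combined protocol and SAP bear on dosing after an infusion reaction.

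- **Section 5.1.7.2 (infusion reactions)** uses mild, moderate and severe tiers defined by symptoms. The severe tier opens "For severe symptoms (e.g., any reaction such as bronchospasm, generalized urticaria, systolic blood pressure <80 mm Hg, or angioedema" and its last dosing instruction is "No further ipilimumab will be administered". The moderate tier takes "any symptom not listed above [mild symptoms] or below [severe symptoms"; if symptoms return when the infusion is resumed, "no additional ipilimumab should be administered that day", and then "The next dose of ipilimumab will be administered at its next scheduled time".
- **Section 5.1.5.1 (permanent discontinuation)** requires a permanent stop for related events at or above "Grade 3 bronchospasm or other hypersensitivity reaction". It adds a stop at any grade where the investigator judges that continued dosing carries substantial clinical risk.
- **Section 5.1.3 (dose modifications)** says a dose may need to be skipped for a related non-skin event of Grade 2 or higher, and must be skipped for a skin event of Grade 3 or higher. If the event has settled to Grade 1 or lower, or to baseline, within the dosing window, the instruction is to "restart ipilimumab dosing at the next scheduled time point per protocol".

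No section maps the tiers of 5.1.7.2 to CTCAE grades, and none states which section takes precedence.

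**The concern.** The decision at issue is whether to give the drug again after a hypersensitivity-type reaction. One section decides it by the symptom's name and the other by its grade. Where the two triggers do not coincide, a clinician can follow the protocol faithfully and reach either answer, and the two participating sites could treat the same reaction differently.

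Patient safety comes first. Exposure comes second: the regimen is eight doses, so a reaction at dose 1 leaves 8 − 1 = 7 that would be given or withheld according to the section followed. Seven is a ceiling, because the last four doses go only to men without radiographic progression. Third, the per-protocol set in Section 8.4 depends on receiving the drug as the protocol prescribes. For such a man, that is not settled.

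**Working it through.** No arithmetic decides this point. The check applies each section in turn to the same event: a reaction during infusion, related to ipilimumab, resolved before the next scheduled dose.

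| Event | 5.1.7.2 | 5.1.5.1, mandatory criterion | 5.1.3 |
|---|---|---|---|
| Bronchospasm, Grade 2 | No further drug | Not met | May be skipped; restarts on resolution |
| Generalized urticaria, Grade 2, classed as non-skin | No further drug | Not met | May be skipped; restarts on resolution |
| Generalized urticaria, Grade 2, classed as skin | No further drug | Not met | No skip required below Grade 3; next dose due |
| Either, Grade 3 or higher, as a hypersensitivity reaction | No further drug | Met: permanent stop | Not needed: the other two agree |

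Three features of the text support the 5.1.7.2 column.

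1. **The severe tier carries no grade.** Its wording is "any reaction such as bronchospasm, generalized urticaria", followed by other examples. Hypotension is divided between the moderate and severe tiers by a systolic pressure of 80 mm Hg; bronchospasm has no such dividing line.
2. **A listed symptom cannot move down a tier.** The moderate tier excludes whatever is listed as severe, so a milder bronchospasm has no other place in 5.1.7.2.
3. **The severe-tier stop has no time limit.** The moderate tier spells out a same-day stop and then says the next dose goes ahead. The severe tier does neither, so it reads most naturally as permanent.

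The Grade 3 threshold for bronchospasm in 5.1.5.1 also implies that the authors had lower grades in mind; otherwise it would exclude nothing.

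The direct conflict is therefore between 5.1.7.2 and 5.1.3, below Grade 3. From Grade 3 upward, 5.1.7.2 and 5.1.5.1 lead to the same result.

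**The case against.** **Severe may simply mean Grade 3 or above.** The listed symptoms are examples, and the diarrhea grading in Appendix 4 pairs mild, moderate and severe with Grades 1, 2 and 3 when it describes ostomy output. On this reading the conflict disappears. It is a possible intention, but 5.1.7.2 states no grade, its wording covers any reaction of the named kinds, and listed symptoms are kept out of the moderate tier. If it is what was meant, it needs to be written down.

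**The stop may be for that day only.** This too would remove the conflict. The contrast with the moderate tier's wording is against it, but the sentence does not say so outright.

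**Section 5.1.5.1 is not contradicted.** A reader might infer that it permits a permanent stop only from Grade 3, which would put all three sections at odds. The text does not support that. It sets a mandatory minimum and adds a stop at any grade on the investigator's judgment, so a stricter rule elsewhere does not breach it. This part of the objection stands. The discretion does not, however, reconcile a flat bar with a restart instruction.

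**Section 5.1.3 is softer than it looks.** A reader might also infer that its Grade 2 hold-and-restart rule plainly covers both named symptoms. It does not. The Grade 2 trigger is permissive and limited to non-skin events, so it fits bronchospasm but reaches urticaria only if that is classed as non-skin. This stands. If urticaria is classed as skin, the next dose is due because nothing requires a skip, which still differs from 5.1.7.2.

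**There are cues to precedence.** Section 5.1.7.2 sits under a guidance heading and calls its content recommendations, whereas 5.1.3 says its own criteria determine delay, restart and discontinuation. Against that, 5.1.7.2 is the more specific section and is worded as a flat bar. The cues point both ways.

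**Conclusion.** The point holds for resolved infusion-related bronchospasm below Grade 3: 5.1.7.2 and 5.1.3 give opposite instructions. Generalized urticaria below Grade 3 is similarly unclear, and there the route through 5.1.3 depends on how the event is classed. Section 5.1.5.1 contributes only a different trigger.

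The conclusion assumes that the severe tier means what it literally says: named symptoms at any grade, and a stop without a time limit. Either alternative reading discussed above would remove the conflict, but the text establishes neither.

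The size is modest. The documents give no rate for these reactions. Section 5.1.7.2 regards allergic reactions as less likely with this antibody, and the list in Section 1.3.4.2 of drug-related serious events in at least 1% of 675 subjects at 10 mg/kg names no bronchospasm, urticaria or hypersensitivity, though it would not capture non-serious events. Few of the 30 planned men are likely to be affected.

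A reader might infer that the inconsistency threatens the trial's main result. It does not bear on the sample size or the error rates, and Section 8.4 uses the intention-to-treat population, where possible, for the primary endpoint. Per-protocol membership, a secondary matter, is left unclear for any affected man. The reason to act is patient safety and consistent dosing.

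**What to change.** Reconcile Sections 5.1.3, 5.1.5.1 and 5.1.7.2 in one amendment that:

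- names one governing section for hypersensitivity and infusion reactions, with cross-references from the other two;
- states one trigger, either named symptoms or CTCAE grade, or maps the tiers of 5.1.7.2 explicitly to grades;
- says whether the severe-tier stop is permanent or for that day.

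Which trigger and which consequence to adopt is for the investigator and the drug supplier to decide; this review takes no position on it. The cost is amendment wording only, with no change to sample size or analysis.

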5.1.7.3 Treatment of Ipilimumab-Related Isolated Drug Fever

In the event of isolated drug fever, the investigator must use clinical judgment to determine if the fever is related to the ipilimumab or to an infectious etiology. If a patient experiences isolated drug fever, for the next dose, pre-treatment with acetaminophen or non-steroidal anti-inflammatory agent (investigator discretion) should be instituted and a repeated antipyretic dose at 6 and 12 hours after ipilimumab infusion, should be administered. The infusion rate will remain unchanged for future doses. If a patient experiences recurrent isolated drug fever following premedication and post dosing with an appropriate antipyretic, the infusion rate for subsequent dosing should be decreased to 50% of the previous rate. If fever recurs following infusion rate change, the investigator should assess the patient's level of discomfort with the event and use clinical judgment to determine if the patient should receive further ipilimumab.

5.2 Prohibited and Restricted Therapies During the Study

5.2.1 Prohibited Therapies

Patients in this study may not use vaccines for the treatment of cancer or prevention of disease unless indicated as a component of the protocol regimen (including those for common medical conditions) for up to one month pre and post dosing with ipilimumab. Concomitant systemic or local anti-cancer medications or treatments are prohibited in this study while receiving ipilimumab treatments.

Patients may not use any of the following therapies during the study:

- Any non-study anti-cancer agent (investigational or non-investigational)
- Any other investigational agents
- Any other (non-CA184024 related) CTLA-4 inhibitors or agonists
- CD137 agonists
- Immunosuppressive agents
- Immunostimulant agents, other than study medication
- Chronic systemic corticosteroids
- Any non-oncology vaccine therapies used for the prevention of infectious diseases (for up to 30 days prior to or after any dose of study drug).
- Any radiation therapies
- Any herbal product known to decrease PSA (eg., Saw Palmetto, PC-SPES)

5.2.2 Restricted Therapies

If a patient enters the trial on AST that consists of a LHRH agonist and an oral antiandrogen, both agents should be continued throughout the study. Patients entering the trial may have stopped previous AST before starting this study for various reasons including but not limited to: AEs related to AST therapy, disease progression on AST, or at the discretion of the treating physician. If an antiandrogen is stopped prior to study entry, it should be stopped 4 weeks before for nilutamide and flutamide and 6 weeks before for bicalutamide to ensure that a withdrawal phenomenon does not interfere with interpretation of efficacy results.

5.2.3 Precautions

Caution is advised when considering treatment with high-dose IL-2 in patients who have previously been administered ipilimumab, particularly in patients who experienced ipilimumab-related diarrhea/colitis. Colonoscopy or sigmoidoscopy with biopsy may be advisable prior to IL-2 administration once the patient is no longer receiving ipilimumab. Notably, IL-2 is not currently used for prostate cancer.

6 STUDY PROCEDURES AND OBSERVATIONS

6.1 Time and Events Schedule for Protocol CA184059

		Induction* (Cycles 1-4)			Between Treatments			Maintenance* (Cycles 5-8)			Every 6 Month Follow Up*		
T //P 1	Scree . #	Wk	Wk	Wk	Wk	Wk	Wk	Wk	11/1 24	WI 26	XX/1 40	W/I (0	Evel Fc
Test / Procedure	ning#	1	4	/	10	12	18	23/24	Wk 24	Wk 36	Wk 48	Wk 60	Π
Informed Consent	X												
Inclusion / Exclusion Criteria	X												
Demographics, medical history, concurrent medical conditions	X												
Testosterone level	X												
Serum samples for hepatitis panel and HIV, if high index of suspicion	X												
ECOG performance status	X	X	X	X	X	X	X	X	X	X	X	X	
Blood collection for correlative studies ¹		X	X	X	X								
Physical Exam	X	X	X	X	X	X	X	X	X	X	X	X	
Vital Signs	X	X	X	X	X	X	X	X	X	X	X	X	
Weight		X	X	X	X				X	X	X	X	
Bone Scan ²	X					X		X		X	X	X	
Chest, Abdomen & Pelvis CT ²	X					X		X		X	X	X	

CBC with differential	X	X	X	X	X	X	X	X	X	X	X	X	
Chemistry Panel: Creatinine, BUN, electrolytes (sodium, potassium, chloride), glucose, bilirubin alkaline phosphatase, ALT, AST, calcium, ³	X	X	X	X	X	X	X	Х	Х	X	Х	X	
LDH	X												
Autoimmune Profile: TSH, free T4	X	X	X	X	X				X	X	X	X	
PSA ⁴	X	X	X	X	X	X	X	X	X	X	X	X	
Concurrent medications (include documentation of androgen suppression therapy)	X	X	X	X	X				X	X	X	X	
Adverse Effects Recorded	X	X	X	X	X		_		X	X	X	X	
Ipilimumab		X	X	X	X				X	X	X	X	
Telephone Contact													X

^{*} Cycle 1-8 procedures can be done +/- 3 days and Long Term Follow-Up can be done +/- 2 weeks.

#Screening procedures must be done within 28 days of first treatment

^{**}PSA, Autoimmune profile, LDH, CBC Diff, Chem panel including Creatinine, BUN, electrolytes (sodium, potassium, chloride), glucose, bilirubin, alkaline phosphatase, ALT, AST, calcium, phosphorus and Correlative **baseline samples** DO NOT need to be repeated on Cycle 1 Day 1 if done within 7 Days of Cycle 1 Day 1

¹ Per outlined correlative studies

² Imaging Studies will also be done every three months until radiographic progression

³ Available labs (i.e. chemistries and blood counts) will be reviewed prior to each infusion

⁴ PSA will be done until radiographic progression

6.2 Procedures by Visit

The Time and Events Schedule summarizes the frequency and timing of various measurements.

6.2.1 Study Completion or Early Discontinuation Visit

At the time of study early withdrawal, the reason for early withdrawal and any new or continuing adverse events should be documented.

